25.13 SERIOUS ADVERSE EVENTS

25.13.1 Definition of a Serious Adverse Event (SAE)

A SAE is an adverse event occurring at any dose that results in any of the following outcomes or actions:

- death

- a life-threatening adverse event (*i.e.*, the patient was at immediate risk of death from the event as it occurred); does not include an event that, had it occurred in a more severe form, might have caused death
- in-patient hospitalization or prolongation of existing hospitalization means that hospital inpatient admission and/or prolongation of hospital stay were required for treatment of an adverse event, or that inpatient hospitalization and/or prolongation of existing hospital stay occurred as a consequence of the adverse event. In general, hospitalization signifies that the participant has been admitted (usually involving at least an overnight stay) at the hospital or emergency ward for observation and/or treatment that would not have been appropriate in the physician's office or outpatient setting. Complications that occur during hospitalization are AE. If a complication prolongs hospitalization or fulfills any other serious criteria, the event is serious. When in doubt as to whether "hospitalization" occurred or was necessary, the AE should be considered serious. Hospitalizations scheduled for an elective procedure or for treatment of a pre-existing condition that has not worsened during participation in the study will not be considered SAEs.
- a persistent or significant disability/incapacity (refers to a substantial disruption of one's ability to conduct normal life functions). The term disability means a substantial disruption of a person's ability to conduct normal life functions. This definition is not intended to include experiences of relatively minor medical significance such as uncomplicated headache, nausea, vomiting, diarrhea, influenza, and accidental trauma (e.g., sprained ankle) which may interfere with or prevent everyday life functions but do not constitute a substantial disruption.
- a congenital anomaly/birth defect
- an important medical event that may not result in death, be life-threatening, or require hospitalization, but may jeopardize the patient and may require medical intervention to prevent the outcomes listed in this definition. Medical or scientific judgment should be exercised by the Investigator in deciding whether SAE reporting is appropriate in other situations such as significant medical events that may jeopardize the participant or may require medical or surgical intervention to prevent one of the other outcomes listed in the above definition. These events should usually be considered serious. Examples of such events include invasive or malignant cancers, intensive treatment for allergic bronchospasm,

blood dyscrasias, convulsions, or development of intervention dependency or intervention abuse.

- An adverse event that does not meet any of the criteria for seriousness listed above will be regarded as a non-serious adverse event.

25.13.2 Serious criteria pertaining to hospitalization should include the following:

- Any formal inpatient admission (even if less than 24 hours).
- Chronic or long-term inpatient admission: transfer within the hospital to an acute/intensive care inpatient unit (e.g., from the psychiatric wing to a medical floor, from a medical floor to the coronary care unit)

Serious criteria pertaining to hospitalization should NOT include the following:

- Emergency Room visits
- Outpatient/same-day/ambulatory procedures and observation/short- stay units
- Hospice facilities and Respite care (e.g., caregiver relief)
- Rehabilitation facilities, skilled nursing facilities, nursing homes, custodial care facilities.

The study period for the purposes of serious adverse event reporting is defined as the period from when the patient provides written informed consent to participate in the study until the patient completes the end of the follow-up period or withdraws from the study.

25.13.3 Expectedness

- A SAE that is not included in the Adverse Reaction section of the relevant reference safety information by its specificity, severity, outcome, or frequency is considered an unexpected adverse event.

25.13.4 Regulatory Reporting Requirements for SAEs

Sponsor is acting on behalf of AstraZeneca for the purposes of safety reporting for this study.

- Prompt notification by the Investigator to Sponsor of an SAE is essential so that legal obligations and ethical responsibilities towards the safety of participants and the safety of study intervention under clinical investigation are met.
- Sponsor has a legal responsibility to notify AstraZeneca, local regulatory authorities and other regulatory agencies about the safety of a study intervention under clinical investigation. Sponsor will comply with country-specific regulatory requirements relating to safety reporting to the regulatory authority, Institutional Review Boards (IRB)/Independent Ethics Committees (IEC), and Investigators.

- An Investigator who receives an Investigator Safety Report describing an SAE or other specific safety information (e.g., summary or listing of SAEs) as outlined in the ESRP will review and then file it along with the Investigator Brochure. The Sponsor will notify the IRB/IEC, if appropriate according to local requirements.
- Investigator Safety Reports must be prepared for Suspected Unexpected Serious Adverse Reactions (SUSAR) according to local regulatory requirements and AstraZeneca policy and forwarded to Investigators as necessary.

25.13.5 Deaths

- All deaths will be SAEs and will require completion of the SAE Report Form. This form includes questions regarding cardiovascular (including sudden cardiac death) and non-cardiovascular death.
- The Death related SAE form should be completed after the occurrence or outcome of death is reported. Initial and follow-up reports regarding death must be completed within one week of when the death is reported.

25.13.6 Investigator Responsibility

To satisfy regulatory requirements, all SAEs that occur during the study (including the protocol-defined follow-up period) regardless of judged relationship to treatment with study product must be reported to MediMergent by the investigator within 24-hours of when the investigator learns about it or, if the event occurs on a weekend or national holiday, on the next working day. The following information should be provided to record the event accurately and completely:

- study name or number
- investigator and study site identification
- patient number
- patient initials
- name of SAE(s)
- investigator's assessment of the relationship of the SAE to the study drug (no reasonable possibility or reasonable possibility)
- Additional information may include the following:
 - age and gender of patient
 - date of study drug administration

- date and amount of administered dose of study product
- onset date and end date of SAE
- description of clinical course of SAE
- action taken
- outcome if known
- severity
- concomitant therapy (including doses, routes, and regimens) and treatment of the event
- pertinent laboratory test data, or other diagnostic test data
- medical history
- if the adverse event results in death
 - cause of death (whether or not the death was related to study product)
 - autopsy findings (if available).

The investigator must ensure that the IRB is also informed of the event in accordance with local regulations.

Note: Although pregnancy is not a SAE, the process for reporting a pregnancy is the same as that for reporting a SAE but using the pregnancy form.

25.14 Disease-Related Events and/or Disease-Related Outcomes Not Qualifying as AEs or SAEs

Adverse events related to signs, symptoms or positive RT-PCR testing for SARS-CoV-2 infection, and/or resulting in hospitalization should be reported as an AE or SAE. If the Investigator considers that there was a causal relationship between treatment with AZD7442 or protocol design/procedures and a patient's underlying disease progression, then this must be reported as an AE or SAE.

For example, the following constitute events meeting the AE definition and that should be considered as expected progression, signs, or symptoms of COVID-19:

- hypoxemia requiring supplemental oxygen
- hypoxemia requiring non-invasive ventilation or high flow oxygen devices
- respiratory failure requiring invasive mechanical ventilation or extracorporeal membrane oxygenation (ECMO)

NOTE: If either of the following conditions apply, then the event must be recorded and reported as an AE or SAE (instead of a disease-related event):

- The event is, in the Investigator's opinion, of greater intensity, frequency, or duration than expected for the natural history of the disease, or
- The Investigator considers that there is a reasonable possibility that the event was related to treatment with study treatment(s).

25.15 Adverse Events of Special Interest

Adverse events of special interest are defined in the study protocol as relevant known toxicities as a result of signals observed from previous studies in the non-clinical programs of AZD7442. These will be updated during the course of the study based on accumulating safety data. AESI include:

- Reactions including hypersensitivity reactions occurring on same day as vaccination
- Local injection site reactions
- Coronary Ischemia
- Myocardial Infarction
- Congestive Heart Failure
- Thrombotic events-coronary, cerebral, abdominal, pulmonary or peripheral vascular

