5.4 Vaccination

If a patient wishes to receive an additional dose of Moderna, Pfizer or Janssen vaccine after baseline treatment with AZD7442, they must wait 14 days before receiving any additional vaccine dose. It is not required that the patient's additional vaccine dose be provided from the same manufacturer as their original vaccination. There will be no attempt to balance the number of patients receiving an additional dose of Janssen, Moderna, or Pfizer vaccine. SARS-CoV-2 EUA or FDA approved vaccinations will be performed at a local pharmacy, community health center or health plan location

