8.2 Exclusion Criteria

Patients meeting any of the following criteria will be excluded from study participation:

- Women who are pregnant, breast feeding or of child bearing potential and not using contraception
- Absence of a qualifying type of cancer as defined by standard ICD-10 diagnostic criteria
- Patient receiving only radiation therapy
- Patient with an ECOG performance status of 2 or higher

- Patient with an expected cancer survival of less than 12 months by disease category
- Patient receiving adjuvant endocrine therapy as their only form of therapy for early-stage breast cancer
- Solid tumor patients more than 6 months post treatment and their cancer is considered to be stable or in remission as determined by the Investigator
- AZD7442 administration at any time prior to day of enrollment
- Have a positive test for SARS-CoV-2 antigen performed by either Rapid Test or SARS-CoV-2 RNA by RT-PCR (Polymerase Chain Reaction) less than 90 days prior to enrollment
- Patient with a prior (within 90 days), current, or planned use of any of COVID-19 convalescent plasma, other monoclonal antibodies against SARS-CoV-2 or any other EUA approved SARS-CoV-2 treatment
- Patient with fever >100.0 F, and/or cough, chills, loss of smell or taste or shortness of breath or any other signs or symptoms consistent with COVID-19 within 5 days prior to enrollment
- Patient who has any known active acute respiratory infection
- Patient who has persistent (refractory to treatment for ≥ 14 days) bacterial or fungal infection
- Patient who has a past SARS-CoV-2 infection within 90 days prior to randomization
- Patient who has received vaccination with any dose of Janssen, Pfizer or Moderna COVID-19 vaccine less than 14 days prior to baseline for this study
- Planned use of any investigational, authorized, or approved vaccine for COVID-19 less than 14 days prior to administration of AZD7442 600 mg IM or IV
- Patient who is unwilling to have SARS-CoV-2 RBD-IgG antibody levels drawn at least 5 times
- Patient who is unwilling to receive treatment with IM or IV AZD7442
- Patient who is unwilling to complete baseline and up to 14 follow-up Experience/Clinical Outcome Assessment (COA) surveys.

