9.3 Follow-Up Activities

Follow-Up activities are as follows:

- At Day 180 post-baseline, all patients will be administered a repeat dose of AZD7442 600 mg IM or IV. The window for this treatment will be +/- 5 days from the actual due date. The dose will be administered in the same manner as the baseline dose unless patient circumstances require a different route of administration. All requirements listed above for baseline AZD7442 administration both IV and IM will be followed for the repeat dose including the one-hour post-dose observation period.
- Patients will complete follow-up Patient Experience/COA surveys on days 2, 30, 60, 90, 120, 150, 180, 181, 210, 240, 270, 300, 330 and 360 post-baseline at home. The window for these surveys will be +/- 5 days from the actual survey due date except for day 2 survey which is +5 days only.
*NB - Study participants will complete all surveys via mobile phone, desktop, laptop, tablet computer or via Call Center. The study site is not responsible for patient completion of the surveys.
- Patients will complete QoL assessments on days 2, 30, 90, 180, 270, and 360 post-baseline at home. The window for these assessments will be +/- 5 days from the actual due date except for day 2 assessment which is + 5 days only.
- Site personnel will obtain blood for serum concentration of AZD7442 at days 30, 90, 180, 270 and 360 post-baseline in the office for all patients. The window for these blood draws will be +/- 5 days from the actual due date. All

serum concentration measurements will be sent to PPD Bioanalytical Laboratory in Richmond, VA for analysis.

- Site personnel will obtain blood for RBD-IgG antibody level at days 90, 180, 270 and 360 post-baseline in the office for all patients. The window for these blood draws will be +/- 5 days from the actual due date. All RBD-IgG antibody levels will be sent to LabCorp for analysis.
- Site personnel will obtain blood for T-cell assay at Day 30 post-baseline in the office for all patients and send to Isoplexis in Branford, CT for analysis. A subset of patients will be selected including 120 patients with hematologic malignancy and 60 patients with solid tumors in order to have site personnel obtain blood for repeat T-cell assay at Day 210 post-baseline in the office and send to Isoplexis in Branford, CT for analysis. The window for these blood draws will be +/- 5 days from the actual due date.

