23.4 AZD7442

AZD7442 (Evusheld) is a combination of two long-acting antibodies (LAABs) - tixagevimab (AZD8895) and cilgavimab (AZD1061) - derived from B-cells donated by convalescent patients after SARS-CoV-2 virus. Discovered at Vanderbilt University Medical Center and licensed to AstraZeneca in June 2020, the human monoclonal antibodies bind to distinct sites on the SARS-CoV-2 spike protein and were engineered and optimized by AstraZeneca with half-life extension and reduced Fc receptor and complement C1q binding. The half-life extension more than triples the durability of its action compared to conventional antibodies and could afford up to 12 months of protection from SARS-CoV-2 infection following a single administration. The reduced Fc receptor binding aims to minimize the risk of antibody-dependent enhancement of disease - a phenomenon in which virus-specific antibodies promote, rather than inhibit, infection and/or disease.

Data published in [*Nature*](#) in July 2020 showed in preclinical experiments that LAABs were able to block the binding of the SARS-CoV-2 virus to host cells and protect against infection in cell and animal models of disease.

23.5 AZD7442 Clinical Trial Results:

- AZD7442 is being studied in a comprehensive clinical trial program for both prevention and treatment of SARS-CoV-2 infection in over 9,000 participants. Ongoing trials include **TACKLE COVID-19**, a Phase III treatment trial in an outpatient setting and collaborator treatment trials in outpatient and hospitalized settings. **TACKLE** included 903 participants in a 1:1 randomization AZD7442 to placebo. AZD7442 is the first LAAB with Phase III data to demonstrate benefit in both prophylaxis and treatment of SARS-CoV-2 infection and is easily administered by IM injection. 90% of enrolled participants were from populations at high risk of progression to severe COVID-19, including those with co-morbidities. The primary analysis was based on 822 participants.
- AZD7442 was assessed using both IM and IV administration routes. Positive high-level results from the **TACKLE** Phase III COVID-19 treatment trial showed AstraZeneca's AZD7442, a long-acting antibody (LAAB) combination, achieved a statistically significant reduction in severe SARS-CoV-2 infection or death compared to placebo in non-hospitalized patients with mild-to-moderate symptomatic SARS-CoV-2 infection.

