25.7.5 Recording and Follow-up of AEs and SAEs

- When an AE/SAE occurs, it is the responsibility of the Investigator to review all documentation (e.g., hospital progress notes, laboratory, and diagnostics reports) related to the event. The Investigator will then record all relevant AE/SAE information. It is required for the Investigator to send photocopies or digital files of the participant's medical records to Sponsor in addition to completion of the required AE/SAE form. There may be instances when medical records for certain cases are requested by pharmacovigilance staff. In this case, all participant identifiers, with the exception of the participant number, will be redacted on the copies of the medical records before submission.
- The investigator will attempt to establish a diagnosis of the event based on signs, symptoms, and/or other clinical information. Whenever possible, the diagnosis (not the individual signs/symptoms) will be documented as the AE/SAE.
- After the initial AE/SAE report, the Investigator is required to proactively follow each participant at subsequent visits/contacts. All SAEs and non-serious AEs of special interest will be followed until the event is resolved, stabilized, otherwise explained, or the participant is lost to follow-up. Further information on follow-up procedures is given in this document.
- The Investigator is obligated to perform or arrange for the conduct of supplemental measurements and/or evaluations as medically indicated or as requested by pharmacovigilance to elucidate the nature and/or causality of the AE or SAE as fully as possible. This may include additional laboratory tests or investigations, histopathological examinations, or consultation with other health care professionals. If a participant dies during participation in the study or during a recognized follow-up period, the Investigator will provide sponsor with a copy of any post-mortem findings including histopathology. New or updated information will be recorded in the participant's medical record and submitted as supplemental information to the original report. The Investigator will submit any updated SAE data to the sponsor or designee within 24 hours of receipt of the information.

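### Section 25.15 times its only hypersensitivity event of special interest to vaccination, not to AZD7442 dosing, so a literal reading leaves out reactions to the study drug

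*Protocol*

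**What the plan says.** Section 25.15 of the protocol describes AESIs as "relevant known toxicities as a result of signals observed from previous studies in the non-clinical programs of AZD7442". The first item in its list is "Reactions including hypersensitivity reactions occurring on same day as vaccination". The remaining items are local injection site reactions, coronary ischemia, myocardial infarction, congestive heart failure and thrombotic events.

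Section 25.7.5 attaches a duty to the label: "All SAEs and non-serious AEs of special interest will be followed until the event is resolved, stabilized, otherwise explained", or until the participant is lost to follow-up.

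On vaccination, section 5.4 says of patients who want a further COVID-19 vaccine dose after baseline treatment that "they must wait 14 days before receiving any additional vaccine dose", and that "SARS-CoV-2 EUA or FDA approved vaccinations will be performed at a local pharmacy, community health center or health plan location". Section 8.2 excludes anyone who has had a dose of Janssen, Pfizer or Moderna "vaccine less than 14 days prior to baseline for this study".

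On the study drug, section 23.4 describes AZD7442 as a combination of two long-acting monoclonal antibodies. It is given at baseline, and section 9.3 adds: "At Day 180 post-baseline, all patients will be administered a repeat dose of AZD7442 600 mg IM or IV", with a window of 5 days either side.

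**The concern.** An AESI list should pick out the reactions that the sponsor wants watched most closely for this product. Here the trigger for the hypersensitivity item is a different act from giving the product. The wording would suit a trial in which the study product is itself a vaccine.

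The label has a practical effect. It is what gives a non-serious event the explicit follow-up endpoint in 25.7.5. The protocol also treats allergic reactions as important: section 1.1 notes isolated anaphylaxis with authorized monoclonal antibodies, section 8.2 excludes patients with a prior severe allergy to the components, and section 9.2 requires observation after dosing. With up to 75 sites, some may follow the wording and others the presumed intention, and coding would then be inconsistent.

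**Working it through.** No sample size, power or error rate is involved, so this is a cross-reading of the definition against the rules around it.

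**1. What vaccination means.** In sections 5.2, 5.4, 8.1, 8.2 and 9.1 the word refers to a Janssen, Moderna or Pfizer COVID-19 product, which 5.4 places at a pharmacy, community health center or health plan location. The study drug is described as administered, at the study visit. The two terms name different acts.

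**2. Can the two days coincide at baseline?** Count the baseline dose as day 0. Section 8.2 allows a prior vaccine only at day −14 or earlier. Section 5.4 allows a later one only from day +14. The permitted vaccination days therefore exclude day 0 and the 13 days on either side of it. In a compliant patient, the day of vaccination is never the baseline dosing day.

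**3. Can they coincide at the repeat dose?** The window of 180 ± 5 gives Days 175 to 185. The 14-day wait in 5.4 is worded around baseline treatment, and nothing brings a vaccine onto the repeat-dose day. An overlap there would be chance.

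**4. Two illustrative events, read literally.**

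| Non-serious event | This AESI under 25.15? | Reportable under 25.8? |
|---|---|---|
| Hives 20 minutes after the baseline AZD7442 dose, reported on the survey | No | Yes, first 24 hours after dosing |
| Hives on the day of a booster at Day 30, no unplanned visit | Yes | Not on the restricted list, unless it counts as a COVID-19 symptom |

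The special-interest item includes an event that 25.8 may not report, and leaves out one that 25.8 is built to capture.

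**5. Does another section repair it?** Section 25.16 covers hypersensitivity but refers to local guidelines and sets no AESI timing. No other listed item covers a systemic allergic reaction to AZD7442.

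**6. What is lost.** Sections 18.6 and 25.4 require follow-up of AEs that are serious, considered related, or the cause of discontinuation. Two things remain uncovered:
- for non-serious reactions judged related, the explicit endpoint of following until resolved, stabilized or otherwise explained;
- for non-serious reactions not judged related, any specific duty beyond the general one in 25.7.5 to follow participants at later contacts.

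The second group need not be empty. Section 25.12 allows an event to be rated not related if another therapy could readily have produced it, and many of these patients are on active cancer treatment.

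**The case against.** The strongest reply is that this is one wrong word in a list that is not closed. Section 25.15 opens with AZD7442 toxicities, introduces the items as inclusions and says they will be updated, so a sensible reader would count a hypersensitivity reaction to AZD7442. Detection does not depend on the label: there is 60 minutes' observation after each dose, first-24-hour events are AEs, systemic events are solicited by survey (25.7.1), and serious reactions are SAEs. This stands, and it limits the size of the point. It does not make the wording right, because the stated trigger conflicts with the section's own purpose and sites would have to guess the intention.

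A reader might also draw three stronger conclusions that the protocol does not support.
- **That reactions to AZD7442 go unfollowed.** Sections 18.6 and 25.4 require follow-up of related AEs whatever their AESI status.
- **That an AESI table will omit them.** The protocol describes no AESI tabulation or analysis; the term appears only in 25.7.5 and 25.15.
- **That booster reactions will be attributed to AZD7442.** Causality is judged event by event (25.7.7, 25.12), and AESI status assigns none. As the second row above shows, such an event may not be reported at all.

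**Conclusion.** The definition is wrong as written. Its timing contradicts the purpose stated in the same section, and under the protocol's own vaccine rules it cannot apply on the baseline dosing day.

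The effect is confined to AESI classification and the follow-until-resolved standard for non-serious reactions. No endpoint, estimate or test changes. The item bears on about 1,500 baseline doses and, if every patient is redosed, about 1,500 × 2 = 3,000 administrations. How many reactions that would involve cannot be stated, because the protocol gives no reaction rate.

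The conclusion assumes that vaccination in 25.15 carries the meaning it has in the rest of the protocol, that patients keep to the 14-day rules, and that sites apply the item literally. Where sites read the intention instead, the practical loss shrinks to inconsistency between sites. The correction is worth making because this is a safety definition and the cost is very small.

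**What to change.** In 25.15, replace the vaccination timing with timing tied to each AZD7442 administration, for example: reactions, including hypersensitivity reactions, within the first 24 hours after any AZD7442 administration. This matches the window already used in 25.7.2 and 25.8.

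Do not name study days. With the ±5-day window in 9.3, an item fixed to Day 180 would miss reactions to doses given on Days 175 to 179 or 181 to 185. Do not add separate collection of vaccine reactions: it is not needed to correct the item and would go beyond the restricted reporting list in 25.8.

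The cost is one line of protocol text and the matching site and coding instructions. First-24-hour events are already collected, so any reported before the change can be reclassified from existing records. Sites take on the 25.7.5 follow-up endpoint for the non-serious reactions that now qualify. No dosing, observation or vaccine-interval rule changes.
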